13.2 Safety review

This study will have a planned safety review after the recruitment of the first 50 participants in Groups 4 and 5. During this review safety reporting information will be reviewed by the DMSC. The safety review will include data up to 30 days after the second vaccination point (visit 3). The DMSC will determine whether the trial should continue. No formal statistical analysis will be performed at this review.

13.3 Stopping rules

The trial can be put on hold upon advice of the DMSC, Chief Investigator, Study Sponsor, regulatory authority, REC, for any single event or combination of multiple events which, in their professional opinion, jeopardise the safety of the participants or the reliability of the data.

13.4 Plan of analysis – primary and secondary outcomes

Analyses will be performed on an intention-to-treat basis and will be directed by a pre-specified statistical analysis plan (SAP). Results will be reported in accordance with CONSORT reporting guidelines.^{10, 11}

Co-primary and secondary immunogenicity outcomes will be analysed using a mixed regression model, with treatment group, age group (50-64, 65-70, 71-74 and 75+ years) and baseline values fitted as fixed effects and centre fitted as a random effect, where possible.

The analysis of the co-primary and secondary safety outcomes will be descriptive only. The number and percentage of participants in each group experiencing each safety outcome will be reported.

Days off work will be analysed using Poisson regression. Quality of life scores (EQ-5D) will be analysed using a mixed regression model, with treatment group, time point (day/visit at which the questionnaire was completed), age group and baseline EQ-5D score fitted as fixed effects and centre fitted as a random effect, where possible. An interaction between treatment group and time point (day/visit) will be included to enable the treatment effects of interest to be estimated.

Two subgroup analyses are planned. The first will be comparing anti-S Ig by COVID-19 vaccine in previous 6 months (yes/no); and the second will be comparing HAI by influenza vaccine in previous 6 months (yes/no). A third subgroup analysis will be considered if a significant number of participants in groups 2 and 3 have a COVID-19 infection between visit 1 and visit 3, comparing anti-S Ig between those who have had a COVID-19 infection between visits 1 and 3 and those who haven't.

Full details of the proposed models will be specified in the SAP. Model validity will be checked using standard methods; alternative models or transformations will be explored if model fit is inadequate. Findings will be reported as effect sizes and 95% confidence intervals.

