Here we propose to evaluate the immunogenicity and safety of RZV co-administered with an mRNA COVID-19 vaccine or an adjuvanted influenza vaccine and describe immunological mechanisms underlying potential vaccine synergy and cross-protection and describe attitudes to co-administration.

3. Aims and objectives

The ZosterFluCov trial aims to evaluate whether RZV can be co-administered with an mRNA COVID-19 (C19) vaccine or an adjuvanted influenza vaccine (aQIV) without an unacceptable increase in reactogenicity or decrease in the immunogenicity of the COVID-19, influenza or RZV vaccines.

Co-Primary Objectives

Part A: Assessment of co-administration of COVID-19 and RZV

1. Immunogenicity, measured by S-binding total Ig, 1 month after COVID-19 mRNA reinforcing dose (Bivalent) vaccine for both strains included in the vaccine given alone compared to co-administration with RZV (1st or 2nd dose).

2. Immunogenicity of 2 doses of RZV vaccine, 1 month after the second dose, given alone, compared to co-administration with C19 with either 1st or 2nd dose of RZV.
3. Rate of grade 3 and 4 solicited systemic adverse reactions over 7 days after 1st and 2nd doses of RZV given alone compared to co-administration with Bivalent vaccine.

Part B: Assessment of co-administration of adjuvanted influenza vaccine and RZV

1. Immunogenicity, measured by haemagglutination inhibition assay, 1 month after adjuvanted influenza vaccine (aQIV) for 3 of the strains included in the vaccine; HAI influenza A H3N2, HAI influenza A H1N1 and HAI influenza B Victoria given alone compared to co-administration with RZV.
2. Immunogenicity of 2 doses of RZV vaccine when given alone, 1 month after the second dose compared to co-administration with aQIV with either 1st or 2nd dose of RZV.
3. Rate of grade 3 and 4 solicited systemic adverse reactions over 7 days after 1st and 2nd doses of RZV given alone compared to co-administration with aQIV.

Key Secondary Objectives

1. Cell-mediated responses to 2 doses of RZV, 1 month after the 2nd dose, given alone compared to co-administration with C19 vaccine with 1st or 2nd dose of RZV.
2. Exploratory evaluation of CD4+T-cells against COVID-19 after vaccination with RZV or aQIV in the CMI cohort.
3. S and N- protein immunoglobulin, before and 1 month after first vaccination in the exploratory immunology cohort.

4. Solicited systemic AEs over 7 days after 1st and 2nd doses of RZV given alone compared to co-administration with either C19 vaccine or aQIV.

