4.1 Primary outcome

Part A: Assessment of co-administration of COVID-19 and RZV

Co-Primary Endpoints

1) Immunogenicity of C19

Anti-S protein Ig concentrations expressed as Geometric Mean Concentrations (GMCs) for both strains in C19 vaccine/RZV (first or second dose, groups 2 & 3) and C19 vaccine alone (group 1), will be used to calculate between group ratios expressed a geometric mean ratio (GMR), at 1 month after vaccination with C19 vaccine.

2) Immunogenicity of RZV

Anti-gE Ig concentrations expressed as GMCs after co-administration of C19 vaccine/RZV (first or second dose) and RZV alone, 1 month after 2nd dose of RZV, and between-group ratios expressed as GMRs.

Success criteria:

Part A of the trial will be classified as a success if both of the following meet the success criteria:

- 1) The combined administration of C19 vaccine and RZV (first or second dose) will be considered non-inferior to C19 vaccine alone if the lower limit of the 95% confidence interval for the (GMR) of anti-S protein Ig concentrations exceeds 0.67, the standard WHO non-inferiority margin for recommendation of new vaccines.⁷, AND

2) The combined administration of C19 vaccine and RZV (first or second dose) will be considered non-inferior to RZV alone if the lower limit of the 95% confidence interval for the GMR of Anti-gE Ig concentrations exceeds 0.67.

3) Safety of RZV

The rate of grade 3 and 4 solicited systemic adverse reactions (Table 2) after C19 vaccine/RZV (first or second dose, groups 2 and 3) and RZV alone 7 days after vaccination (groups 1-5) This is a descriptive outcome.

Table 2 Solicited AEs collected on post vaccination diary cards

Systemic solicited AEs
Fatigue
Fever
GI symptoms†
Headache
Myalgia
Shivering

†Gastrointestinal symptoms include nausea, vomiting, diarrhoea and/or abdominal pain

Note: The above AEs are assumed to be related and will be classed as adverse reactions.

Part B: Assessment of co-administration of adjuvanted influenza vaccine and RZV

Co-Primary Endpoints

1) Immunogenicity of aQIV

HAI titres expressed as GMCs in aQIV/RZV (first or second dose, groups 4 & 5) and aQIV alone (group 3) will be used to calculate between group ratios, expressed as GMR at one month after aQIV vaccination.

2) Immunogenicity of RZV

Anti-gE Ig concentrations expressed as GMCs after co-administration of aQIV/RZV (first or second dose) and RZV alone, 1 month after 2nd dose of RZV, and between-group ratios expressed as GMRs.

Success criteria:

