Part B of the trial will be classified as a success if both of the following meet the success criteria:

- 1) The combined administration of aQIV and RZV (first or second dose) will be considered non-inferior to aQIV (for 3 of the strains included in the vaccine; HAI influenza A H3N2, HAI influenza A H1N1 and HAI influenza B Victoria) alone if the lower limit of the 95% confidence interval for the GMR of HAI exceeds 0.67, the standard WHO non-inferiority margin for recommendation of new vaccines.⁷, AND
- 2) The combined administration of aQIV and RZV (first or second dose) will be considered non-inferior to RZV alone if the lower limit of the 95% confidence interval for the GMR of Anti-gE Ig concentrations exceeds 0.67.

3) Safety of RZV

The rate of grade 3 and 4 solicited systemic adverse reactions (Table 2) after aQIV/RZV (first or second dose, groups 4 and 5) and RZV alone 7 days after vaccination (groups 1-5). This is a descriptive outcome.

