4.2 Secondary outcomes

Immunological

- Vaccine response rate (VRR) to RZV as measured by anti-gE, 1 month after vaccination with 2nd dose of RZV, in all groups and between-group differences. VRR defined as a 4-fold increase in post-vaccination anti-gE compared to pre-vaccination anti-gE

concentration for participants who are seronegative at baseline then a 4-fold increase compared to a cut-off value for seropositivity.

- Exploratory evaluation of cell-mediated immunology, CD4+T-cells responses 1 month after the 2nd dose of RZV as measured by intracellular cytokine staining (ICS) compared to RZV given alone or concomitantly for either first or second dose
- S and N-protein immunoglobulin, before and 1 month after vaccination with a single dose of RZV and aQIV to assess for exploratory immunology T-cells against SARS-CoV-2 provided by RZV vaccine or aQIV

Safety

- Percentage of participants reporting grade 3 and 4 SSR after first dose of RZV alone compared to first dose co-administered with either C19 vaccine or aQIV.
- Percentage of participants reporting grade 3 and 4 SSR after second dose of RZV alone compared to second dose co-administered with either C19 vaccine
- Percentage of participants reporting solicited local and systemic Aes, 7 days after each vaccination time point by group and between-group ratios
- Unsolicited Aes for 30 days after vaccination
- Serious adverse events throughout the study period
- Adverse events of special interest (pIMDs) throughout the study period
- Days off work (for participants in employment) during the study period reported as related to vaccination
- Quality of life score following vaccine co-administration compared to single vaccination in the 7 days after vaccination

Qualitative

Outcomes will include but not be limited to

- Participant acceptance of multiple vaccinations (2 or more) for future routine vaccinations
- Trial staff perceptions on offering multiple vaccinations (2 or more) for future routine vaccinations

5. Plan of Investigation

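### Success in Parts A and B is decided on immunogenicity alone, and the protocol contradicts itself on whether the co-primary grade 3–4 reaction outcome will be compared between RZV alone and co-administration

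*Protocol*

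**What the plan says.** Protocol Section 3 sets an aim with two limbs: co-administration "without an unacceptable increase in reactogenicity or decrease in the immunogenicity of the COVID-19, influenza or RZV vaccines". No figure for an unacceptable increase appears anywhere.

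In both parts a co-primary objective compares grade 3–4 solicited systemic reactions in the week after each RZV dose between RZV by itself and RZV given together with the other vaccine. Section 4.1 repeats this as an endpoint, pooled over first or second dose (Groups 2 and 3 in Part A, Groups 4 and 5 in Part B, against RZV alone in Groups 1–5), and adds: "This is a descriptive outcome".

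Section 4.1 then gives the decision rules: "Part A of the trial will be classified as a success if both of the following meet the success criteria", and "Part B of the trial will be classified as a success if both of the following meet the success criteria". In each part, both criteria are non-inferiority statements on a geometric mean ratio, for example "if the lower limit of the 95% confidence interval for the GMR of Anti-gE Ig concentrations exceeds 0.67".

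Section 13.4 states: "The analysis of the co-primary and secondary safety outcomes will be descriptive only". The output it names is the number and percentage of participants per group. The same section ends by saying, with no exception for safety, that findings will be given as effect sizes with 95% confidence intervals. Section 4.2 lists solicited local and systemic events "7 days after each vaccination time point by group and between-group ratios".

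**The concern.** Three things do not fit together.

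- **Aim and decision rule.** A whole part of the trial is labelled a success or not, yet one of the two limbs of the aim has no input to that label. The label would be the same whatever happened to severe reactions.
- **Objective and analysis.** The co-primary safety objective is a comparison. The analysis sentence specific to it provides only per-group counts, while a lower-ranked secondary outcome is given between-group ratios.
- **Groups and exposures.** A percentage per randomised group is not a percentage per exposure, because most groups have both exposures at different visits.

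At stake is how the reactogenicity limb will be read. Section 18 expects the results to inform government, clinicians and the public on the safety of giving these vaccines together. If the output is a table of percentages, two similar figures invite the reading that there is no increase, with nothing to show how large an increase remains possible.

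**Working it through.** **1. What enters the success rules.** The stated powers confirm the reading of 4.1.

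- Part A (Table 10): n = 95 per group, SD 0.35, margin 0.174 on the log10 scale, one-sided 2.5%. z = 0.174 / (0.35 × √(2/95)) − 1.96 = 3.43 − 1.96 = 1.47, so power is 92.9%, as stated. With two anti-S strains plus anti-gE, 0.9287³ = 0.801, the stated 80.1%.
- Part B (Table 11): 0.807 × 0.9993 = 0.806, the stated 80.6%. The 80.7% for the three HAI outcomes rests on a correlation matrix that is not shown and is taken as given.

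Three outcomes in Part A and four in Part B, all immunological, account for the conjunctive power in full. Safety has no part in it.

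**2. Doses per exposure, from Table 3.** Group sizes are 120, 120, 240, 240 and 240. Only 120 of Group 3 continue to receive RZV.

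| Group | First RZV dose | Second RZV dose |
|---|---|---|
| 1 (120) | alone | alone |
| 2 (120) | alone | with C19 |
| 3 (120 continuing) | with C19 | alone |
| 4 (240) | with aQIV | alone |
| 5 (240) | alone | with aQIV |

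- RZV alone, first dose: 120 + 120 + 240 = 480 (Groups 1, 2, 5). Second dose: 120 + 120 + 240 = 480 (Groups 1, 3, 4). Pooled: 960.
- With C19: 120 first + 120 second = 240 pooled.
- With aQIV: 240 first + 240 second = 480 pooled.

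No group has only co-administered doses, so the comparison has to be assembled across groups and visits. Key secondary objectives 8–11 in Section 3 already do this dose by dose.

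**3. Precision of that comparison.** The documents give no grade 3–4 rate for RZV alone. I assume a rate p of 5–15%, equal under both exposures, with independent doses and no dropout. The 95% half-width is 1.96 × √[p(1−p)(1/n₁ + 1/n₀)].

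Example, Part A pooled at p = 5%: 1.96 × √[0.0475 × (1/240 + 1/960)] = 1.96 × 0.0157 = 3.1 points.

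| Contrast | n₁ v n₀ (doses) | p = 5% | p = 10% | p = 15% |
|---|---|---|---|---|
| Co-primary, Part A | 240 v 960 | 3.1 | 4.2 | 5.1 |
| Co-primary, Part B | 480 v 960 | 2.4 | 3.3 | 3.9 |
| By dose, C19 | 120 v 480 | 4.4 | 6.0 | 7.1 |
| By dose, aQIV | 240 v 480 | 3.4 | 4.6 | 5.5 |

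(percentage points)

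**4. The independence assumption.** Suppose a participant's two RZV doses have correlation ρ. Each co-administered dose is matched by one alone dose in the same person, giving a covariance term of ρ/960. Group 1's 120 pairs of alone doses add 2 × 120 × ρ/960² = ρ/3840 to the variance. The bracket 1/n₁ + 1/n₀ becomes (20 − 7ρ)/3840 in Part A and (12 − 7ρ)/3840 in Part B. Positive correlation would therefore narrow the pooled intervals, while dropout would widen them.

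**The case against.** The strongest reply is that descriptive safety is an open design choice. Section 4.1 says so in each part, 13.4 repeats it, and 13.1 limits the sample size to immunogenicity. Each criterion names exactly what it concludes. The interval method and effect measure normally belong in the SAP, which is not at hand. Descriptive may also mean only that there is no hypothesis test: 4.2 lists days off work and quality of life under safety, yet 13.4 models both by regression.

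Much of this stands, and it rules out several stronger readings that a reader might infer:

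- *That no between-group estimate is planned at all.* Section 4.2 names ratios for solicited events, and 13.4 closes with effect sizes and intervals. The documents support an internal conflict, not a complete absence.
- *That success is meant to establish safety.* No section says this. The defect is that the label covers the whole part while the rule covers one limb of the aim.
- *That a descriptive co-primary safety outcome is an error.* It is not, and no test or safety margin is required.
- *That the by-dose half-widths describe the co-primary outcome.* They belong to the secondary contrasts. The pooled co-primary contrast is more precise.

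Two things remain. The SAP can add intervals, but the success definition and the descriptive-only sentence are fixed in the protocol, and that sentence contradicts other protocol text. DMSC review oversees conduct, with no formal analysis at the planned safety review, and does not evaluate the aim.

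**Conclusion.** The point holds as a mismatch between the aim and the success rule, together with an inconsistency over how the co-primary safety outcome is analysed. Part A or Part B can be classed a success with no reference to grade 3–4 reactions. The analysis sentence specific to that outcome yields figures that do not answer its own comparative objective.

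For the co-primary contrast, the 95% half-width is about 3.1–5.1 points in Part A and 2.4–3.9 in Part B. Relative to the assumed rate, Part A runs from 3.1/5 = 62% down to 5.1/15 = 34%, and Part B from 2.4/5 = 48% down to 3.9/15 = 26%. Equal observed percentages would thus remain compatible with increases of that order. These sizes rest on assumed equal rates of 5–15%, independent doses and full numbers. The inconsistency itself rests on no assumption.

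This should be corrected. It does not undermine the immunogenicity analyses.

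**What to change.** **Section 13.4.** Replace the descriptive-only sentence, for grade 3–4 solicited systemic reactions, with a statement along these lines: the outcome will be reported as a risk difference (co-administered minus RZV alone) with a 95% confidence interval and no hypothesis test, (a) for the pooled first-or-second-dose contrast in each part, allowing for repeated doses within participants, and (b) for the by-dose contrasts in key secondary objectives 8–11. Per-group numbers and percentages can stay alongside. Reconcile the wording with 4.2 and with the section's closing sentence. The choice of interval method can be left to the SAP.

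**Section 4.1.** State that success in Part A or Part B means immunogenicity non-inferiority only, and that any conclusion on reactogenicity will quote the upper confidence limit of the risk difference. Whether to say what increase would be unacceptable is for the sponsor.

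**Cost.** Protocol and SAP wording and a few extra table columns, from data already collected and with no added participants. The downside is that the published intervals will show how large an increase the trial cannot exclude.

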13.5 Frequency of analyses

The analysis of the primary safety outcome will take place when all recruited participants have submitted 7-day diary information, that this has been reviewed at visit 6, the data relating to the 7-day outcomes are checked and complete and that element of the database can be locked.

Analyses of other outcomes will take place when the trial is complete, and the database is locked.

14. Trial management

University Hospitals Bristol and Weston NHS Foundation Trust will act as Sponsor. The BTC will act as the coordinating centre for the trial. Responsibility for running the ZosterFluCov trial will be established via a collaboration agreement with the University of Bristol. Agreements between the Sponsor and participating centres will be required, as well as standard site initiation documents, before recruitment commences. Appropriate contractual arrangements will also be put in place with other third parties.

The trial will be conducted in accordance with GCP guidelines, the Medicines for Human Use (Clinical Trials) Regulations 2004 and subsequent amendments, the Data Protection Act and the UK Policy Framework for Health and Social Care Research. The trial will be registered on an open access clinical trial database (ISRCTN).

Clinical trial documents will be archived and held by the Sponsor for 15 years after trial closure in accordance with the standard operating procedures of the Sponsor and in compliance with the principles of GCP.

The trial will be managed by the Chief Investigator (CI), with mentoring and support from senior members of the research team who will provide experience of implementing large scale clinical trials, and the Trial Managers, with full support from the wider BTC, which is a UK Clinical Research Collaboration registered clinical trial unit (UKCRC Reg. No 70). The BTC has an

established track record of designing, conducting, managing and reporting multi-centre clinical trials.

The CI and coordinating centre team will work with the co-applicants to prepare the final protocol and submit the REC, MHRA and associated Health Research Authority (HRA) applications. The coordinating centre will prepare the trial documents, provide the randomisation service and design and implement the data management system.

The CI, coordinating team and Sponsor will endeavour to ensure that the trial runs according to the agreed timetable, recruitment targets are met, the Case Report Forms (CRFs) are completed accurately, the trial complies with relevant ethical and other regulatory standards, and that all aspects of the trial are performed to the highest quality. The CI and coordinating centre team will also train investigators at participating centres, check that each centre is ready to start (“green light”) and monitor their progress during the trial. The Trial Managers will be the contact point to provide support and guidance to the participating centres throughout the trial.

14.1 Day-to-day management

The ZosterFluCov trial will be managed by a Trial Management Group (TMG), which will meet face-to-face or virtually regularly. The TMG will be chaired by the CI and others will be invited as appropriate (see CI & Research Team Contact Details).

14.2 Monitoring of sites

14.2.1 Initiation training

Before the trial commences, training session(s) will be organised by the coordinating centre. These sessions will ensure that personnel at each site involved fully understand the protocol, e-CRFs, interventions, the operational requirements of the trial and the assessments to be conducted within the trial.

14.2.2 Site monitoring

The trial coordinating centre will carry out regular monitoring and audit of compliance of centres with GCP and data collection procedures. Monitoring of data collection will be via the trial database (checks for data completeness and routine data query review), which will be carried out on a regular basis. The TMG will review accumulating data on, including but not limited to, screening, eligibility, recruitment, data completeness, adherence to trial visits and procedures, adverse events and protocol deviations in the form of central monitoring reports.

